## Appendix 1E - Additional IV Medication for BP Use in China

The drugs listed in this Appendix are additional medications for BP lowering that can be used in China sites.

### 1. *Suggested IV medication for BP lowering*

#### 1) Esmolol

Dosage and administration:

Bolus or infusion: It is recommended that an initial loading dose of 0.5 milligrams/kg body weight (500 micrograms/kg) infused over a one-minute duration, followed by a maintenance infusion of 0.05 milligrams/kg/min (50 micrograms/kg/min) for the next 4 minutes. If it is efficacious, the maintenance infusion may be continued at 0.05 mg/kg/min. If an adequate therapeutic effect is not observed, repeat the same loading dosage and follow with a maintenance infusion. The maintenance infusion may be continued at 0.05 mg/kg/min or increased step wise (e.g. 0.1 mg/kg/min, 0.15 mg/kg/min or a maximum of 0.2 mg/kg/min) with each step being maintained for 4 or more minutes. The maintenance infusion may be increased to a maximum of 0.3 mg/kg/min. Maintenance dosages above 200 µg/kg/min (0.2 mg/kg/min) have not been shown to have significantly increased benefits.

#### 2) Enalaprilat

Dosage and administration:

Therapy should be individualised. For patients on diuretic therapy, the dosage of enalaprilat should be reduced. Dose in hypertension is 1.25 mg every six hours administered intravenously over a five minute period. Doses higher than 5 mg every six hours are not suggested.

### 2. *IV medication for BP lowering which can also be used*

#### 1) Diltiazem

Dosage and administration:

An initial dose of 10 mg or 0.5 mg - 0.25 mg/kg body weight infused within 3 minutes can be used. Diltiazem should be diluted in normal or glucose solutions to a concentration of 1% before use. This dose can be repeated after 15 minutes. A maintenance infusion of 5 µg - 15 µg/kg/min is also permitted.

#### 2) Nitroglyceride

Dosage and administration:

Nitroglyceride injection 10 mg is diluted in 0.9% normal solution 500 ml or 5% glucose solution 500 ml. The initial dose of nitroglyceride is 5 drops/min, and under close BP monitoring may increase by 5 drops/min every 3-5 minutes. If the dose of 20 drops/min is still not efficacious, 10 drops/min can be added every 3-5 minutes. Doses usually can be from 5 to 50 drops/min.

Note: Phosphodiesterase inhibitors must not be used with GTN.

#### 3) Nimodipine

Dosage and administration:

Nimodipine 50 ml/50 mg should be put in a micro pump and infused in a constant speed 4 ml/hour, once a day. Usually it can be used for 5 to 14 days. Then, change to oral nimodipine. However, the BP lowering effect of oral nimodipine is not obvious.

#### 4) Furosemide

Dosage and administration:

The usual initial dose of furosemide is 20-80 mg. If needed, the same dose can be repeated every 2 hours. The total dosage cannot be more than 1 g/d. If it is not effective, the dose should not be increased, to avoid renal toxicity.

## Appendix 1F- BP protocol for centres with Clevidipine

Early intensive BP lowering group	TREATMENT PROTOCOL
INITIAL therapy	
BP Target	SBP 130-140 mmHg reached within 60 minutes of Randomisation into the BP arm
Monitoring	
 
• Continuous HR monitoring
 
• Record BP/HR q 2 mins during active treatment, then q 15 min for first hour, q 30 min for next 5 hours and then hourly to 24 h
 

Clevidipine (Continuous IV Infusion) (requires ICU admission)	
 
• Clevidipine initiation dose: 2 mg/hour continuous IV for the first 1.5minuts
 
• If SBP >140 mmHg, DOUBLE the dose every 2-10 minutes (4, 8, 16 and then 32 mg/hour)
 
• Maximum dose = 32.0mg/hour
 

Hydralazine (IV)	If BP persistently >140 mmHg: 
 
• ADD Hydralazine with a test dose: 5 mg IV bolus over 1 minute
 
• If SBP >140 mmHg, repeat 5 mg IV bolus in 5 minutes
 
• If SBP still > 140mmHg, give 10 mg IV bolus q 5 mins until target SBP reached. Increase to 20 mg bolus if required
 
• Maximum hydralazine dose = 240mg/24 hours
 

Glyceryl Trinitrate (Topical)	If BP persistently >140 mmHg: 
 
• ADD topical glyceryl trinitrate (paste or patch) at a rate of 5-10 mg/24hour (≈200-400 µg/hour). NB: also known as topical nitroglycerin
 

Continuous IV Infusions (requires ICU admission)	If BP persistently >140 mmHg: 
 
• ADD infusion of hydralazine 50-150 µg/min OR glyceryl trinitrate 1-100 µg /min
 

MAINTENANCE therapy	
BP Target	Maintenance of SBP 130-140 mmHg
Monitoring	Once SBP is under target (confirmed by 4 readings 15 minutes apart): 
 
• Record BP/HR q 30 minutes for 5 hours and then q 1 h for 18 h.
 

Continuous IV treatment prn	If SBP exceeds 140mmHg at any point: 
 
• DOUBLE the dose of Clevidipine every 2-10 minutes (4, 8, 16 and then maximum dose of 32 mg/hour)
 
• If SBP is <140mmHg, Keep the dose of Clevidipine
 
• If SBP < 130 mmHg or HR < 55 bpm, then HALVE the dose of Clevidipine every 2-10 minutes and then cease treatment
 
• If HR increases by >15 bpm or is >90 bpm, add IV beta blocker
 

Oral treatment	Start treatment by 24 hours (use nasogastric if required) 
 
• If not contraindicated and no other drug is specifically indicated, start combination therapy of ACEI + diuretics in addition to previous anti-
 

---

hypertensives

**Note: Monoamine oxidase inhibitors are not recommended with this BP lowering agent and phosphodiesterase inhibitors must not be used with GTN.**

**Key to abbreviations:** ACEI – Angiotensin converting enzyme inhibitor; BP – blood pressure; bpm – beats per minute; HR – heart rate; ICU – intensive care unit; q – every; prn – as required; mg/hour – milligram per hour;  $\mu\text{g}/\text{Kg}/\text{min}$  – micrograms per kilogram per minute;  $\mu\text{g}/\text{min}$  – micrograms per minute.

## Appendix 1G - BP protocol for centres with Nicardipine

Early intensive BP lowering group	TREATMENT PROTOCOL
INITIAL therapy	
BP Target	SBP 130-140 mmHg reached within 60 minutes of Randomisation into the BP arm
Monitoring	
 
• Continuous HR monitoring
 
• Record BP/HR q 2 mins during active treatment, then q 15 min for first hour, q 30 min for next 5 hours and then hourly to 24 h
 

Nicardipine (Continuous IV Infusion) (requires ICU admission)	
 
• Nicardipine initiation dose: 5 mg/hour continuous IV for the first 15 minutes
 
• If SBP >140 mmHg, increase the dose by 2.5 mg/hour every 15 minutes (7.5, 10, 12.5 and then 15 mg/hour)
 
• Maximum dose = 15 mg/hour
 

Hydralazine (IV)	If BP persistently >140 mmHg: 
 
• ADD Hydralazine with a test dose: 5 mg IV bolus over 1 minute
 
• If SBP >140 mmHg, repeat 5 mg IV bolus in 5 minutes
 
• If SBP still > 140mmHg, give 10 mg IV bolus q 5 mins until target SBP reached. Increase to 20 mg bolus if required
 
• Maximum hydralazine dose = 240mg/24 hours
 

Glyceryl Trinitrate (Topical)	If BP persistently >140 mmHg: 
 
• ADD topical glyceryl trinitrate (paste or patch) at a rate of 5-10 mg/24hour (≈200-400 µg/hour). NB: also known as topical nitroglycerin
 

Continuous IV Infusions (requires ICU admission)	If BP persistently >140 mmHg: 
 
• ADD infusion of hydralazine 50-150 µg/min OR glyceryl trinitrate 1-100 µg /min
 

MAINTENANCE therapy	
BP Target	Maintenance of SBP 130-140 mmHg
Monitoring	Once SBP is under target (confirmed by 4 readings 15 minutes apart): 
 
• Record BP/HR q 30 minutes for 5 hours and then q 1 h for 18 h.
 

Continuous IV treatment prn	If SBP exceeds 140mmHg at any point: 
 
• INCREASE the dose of Nicardipine by 2.5 mg/hour every 15 minutes (7.5, 10, 12.5 and then 15 mg/hour)
 
• If SBP is <140mmHg, Keep the dose of Nicardipine
 
• If SBP < 130 mmHg or HR < 55 bpm, then DECREASE the dose of Nicardipine by 2.5mg/hour every 2-15 minutes and then cease treatment
 
• If HR increases by >15 bpm or is >90 bpm, add IV beta blocker
 

---

*Oral treatment*

Start treatment by 24 hours (use nasogastric if required)

- If not contraindicated and no other drug is specifically indicated, start combination therapy of ACEI + diuretics in addition to previous anti-hypertensives

**Note: Monoamine oxidase inhibitors are not recommended with this BP lowering agent and phosphodiesterase inhibitors must not be used with GTN.**

**Key to abbreviations:** ACEI – Angiotensin converting enzyme inhibitor; BP – blood pressure; bpm – beats per minute; HR – heart rate; ICU – intensive care unit; q – every; prn – as required; mg/hour – milligram per hour;  $\mu\text{g}/\text{Kg}/\text{min}$  – micrograms per kilogram per minute;  $\mu\text{g}/\text{min}$  – micrograms per minute.

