### **6.1 BP control arm**

#### *6.1.1 Early Intensive BP Lowering Group*

The aim is to achieve a systolic BP level 130-140 mmHg **within 60 minutes** of Randomisation into the BP arm *and* to maintain this BP level for the next 72 hours (or until hospital discharge or death if this should occur earlier). A standardised i.v. BP lowering regimen using locally available and approved i.v. BP lowering agents will be used, commenced in the emergency department and later in a high dependency area (e.g. acute stroke or neurointensive care unit) as is usual for patients receiving rtPA.

BP lowering will be titrated by repeat i.v. bolus or infusion, with a systolic BP of <130 mmHg being the safety threshold for cessation of therapy. It is anticipated that i.v. agents will be required for at least the first several hours in most cases but the timing of switch to oral BP lowering agents will be at the discretion of the responsible clinician according to BP control and patient status. It is also expected that i.v. therapy will continue to be required during the initiation of oral anti-hypertensive therapy, to maintain the systolic BP levels 130-140 mmHg.

When administering BP lowering treatment, care is required to ensure that severe hypotension is avoided in patients by checking first for potential dehydration and providing intravenous fluids.

Since the study seeks to address the impact of BP lowering and not a specific agent, and to ensure the trial result is maximally generalisable to existing routine practice, some flexibility is allowed in the use of locally available i.v. agents (e.g. urapidil, labetalol, hydralazine, metoprolol, clevidipine), but all other aspects treatment are standardised across sites. Patients on prior oral BP lowering agents should have this continued if possible and antihypertensive therapy prescribed when patients are clinically stable as per guidelines for secondary stroke prevention. Investigators are encouraged to adhere to study protocols, provide active care, but are free to modify a patient's treatment as required according to clinical judgment.

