## Appendix 1A - BP management protocol WITHOUT Labetalol

Early intensive BP lowering group	TREATMENT PROTOCOL
INITIAL therapy	
BP Target	SBP 130-140 mmHg reached within 60 minutes of Randomisation into the BP arm
Monitoring	
 
• Continuous HR monitoring
 
• Record BP/HR q 5 mins during active treatment, then q 15 min for first hour, q 30 min for next 5 hours and then hourly to 24 h
 

Hydralazine (IV)	
 
• Hydralazine test dose: 5 mg IV bolus over 1 minute
 
• If SBP >140 mmHg, repeat 5 mg IV bolus in 5 minutes
 
• If SBP still > 140mmHg, give 10 mg IV bolus q 5 mins until target SBP reached
 
• Increase to 20 mg bolus if required
 
• Maximum hydralazine dose = 240mg
 

Metoprolol (IV)	If BP persistently > 140 mmHg: 
 
• ADD Metoprolol 5 mg IV bolus over 3-5 minutes, repeat 5mg bolus in 5 minutes x 2 if necessary but do NOT give if HR<55bpm
 

Glyceryl Trinitrate (topical)	If BP persistently > 140 mmHg: ADD topical glyceryl trinitrate (paste or patch) at a rate of 5-10 mg/24 hour (≈ 200-400 µg/hour). NB: also known as topical nitroglycerin
Continuous IV Infusions (requires ICU admission)	If BP persistently > 140 mmHg: 
 
• Start infusion of hydralazine - 50-150 µg/min
 
• If target still not reached ADD infusion of glyceryl trinitrate 1-100 µg /min
 
• OR start infusion of Nicardipine 5-15 mg/hour
 

MAINTENANCE therapy	
BP Target	Maintenance of SBP 130-140 mmHg
Monitoring	Once SBP is under target (confirmed by 4 readings 15 minutes apart): 
 
• Record BP/HR q 30 minutes for 5 hours and then q 1 h for 18 h
 

IV treatment prn	If SBP exceeds 140mmHg at any point: 
 
• Give Hydralazine 10-20 mg boluses. BP and HR should then be recorded 5 and 15 minutes after each bolus
 
• If SBP is <140mmHg, give further Hydralazine 10-20 mg boluses (dependent on initial dose) q 6 hours for first 24 hours (total of 3 doses)
 
• If SBP < 130 mmHg, cease therapy
 

---

*Oral treatment*

Start treatment by 24 hours (use nasogastric if required)

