IV treatment prn	If SBP exceeds 140mmHg at any point: 
 
• Give Labetalol (20-40 mg) and/or hydralazine (10-20 mg) boluses. BP and HR should then be recorded 5 and 15 minutes later
 
• If SBP is <140mmHg, Labetalol 10-40 mg (dose dependent on initial response) should be administered q 6 hours for the first 24 hours after symptom onset (total of 3 doses)
 
• If SBP < 130 mmHg or HR < 55 bpm, then cease treatment.
 

- Maximum labetalol dose: 300 mg/24 hours
- **Note: labetalol and hydralazine may be used together during the maintenance phase**

*Oral treatment*

Start treatment by 24 hours (use nasogastric if required).

- If not contraindicated and no other drug is specifically indicated, start combination therapy of ACEI + diuretics in addition to previous anti-hypertensives

**Note: Monoamine oxidase inhibitors are not recommended with labetalol. Phosphodiesterase inhibitors must not be used with GTN.**

**Key to abbreviations:** ACEI – Angiotensin converting enzyme inhibitor; BP – blood pressure; bpm – beats per minute; HR – heart rate; ICU – intensive care unit; q – every; prn – as required;  $\mu\text{g}/\text{Kg}/\text{min}$  – micrograms per kilogram per minute;  $\mu\text{g}/\text{min}$  – micrograms per minute.

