## Appendix 1H - BP protocol for centres with Nicardipine (Vietnam)

Early intensive BP lowering group	TREATMENT PROTOCOL
INITIAL therapy	
Indication	SBP > 140 mmHg, then at least 2 times, 5 min apart
BP Target	SBP < 140mmHg reached within 60 minutes of Randomisation into the BP arm
Monitoring	
 
• Continuous HR monitoring
 
• Record BP/HR q 5 mins during active treatment, then q 15 min for first hour, q 30 min for next 5 hours , then hourly for next 18h to 24 h (totally for initial 24h), and then every 3h in next 72h
 

Medication	
Nicardipine (Continuous IV Infusion) (requires ICU admission)	
 
• Nicardipine initiation dose: 5 mg/hour continuous IV for the first 15 minutes
 
• If SBP >140 mmHg, increase the dose by 1-2.5 mg/hour every 5 minutes (7.5, 10, 12.5 and then 15 mg/hour)
 
• Maximum dose = 15 mg/hour
 

Nitroglycerin	If SBP > 140 mmHg after treatment maximum dose of Nicardipine Nitroglycerin dose: 1 – 100 µg /min
MAINTENANCE therapy	
BP Target	Maintenance of SBP 130-140 mmHg/72h
Monitoring	Once SBP is under target (confirmed by 4 readings 15 minutes apart): 
 
• Record BP/HR q 30 minutes for 5 hours and then q 1 h for 18 h.
 

Continuous IV treatment prn	IV infusion according to BP level, increasing or decreasing doses depends on BP stability. If SBP exceeds 140mmHg at any point: 
 
• INCREASE the dose of Nicardipine by 2.5 - 5 mg/2 – 5 minutes
 
• If no reaching SBP target, increase IV infusion maintenance doses (amend 1 – 2.5 mg for each dose increase (e.g if maintenance dose of 2.5 mg/h, dose increased will be 3 – 4.5 mg/h)
 
• If SBP is <140mmHg, Keep the dose of Nicardipine
 
• If SBP < 130 mmHg or HR < 55 bpm: Cease treatment then if SBP≥140 mmHg, repeat the Nicardipine IV infusion with a half of the Dose before ceasing treatment. If SBP still >140 mmHg at maximum dose of Nicardipine, Nitroglycerine is able to be amended.
 

*Oral treatment*

When the BP is stable in 4 consecutive recording times (starting at the 20th hour), oral medications are able to be used.

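### Below 130 mmHg systolic, section 6.1.1 and five drug appendices say cease, while Appendices 1F and 1G order a stepwise reduction first, and no text says which governs

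*Protocol*

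**What the plan says.** Protocol section 6.1.1 describes titration by repeated bolus or by infusion, "with a systolic BP of <130 mmHg being the safety threshold for cessation of therapy". It lets sites choose among locally available agents, clevidipine being one of those named, and says the rest of the treatment is the same everywhere. It mentions no taper and no exception by drug. Its paragraph on intravenous treatment refers the reader to Appendices 1A to 1H without ranking section against appendix.

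Seven of those eight appendices state an action at systolic BP below 130 mmHg (1E has none). They fall into two groups.

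- **Cease, no steps.** Appendix 1A: below "130 mmHg, cease therapy". Appendix 1B: below 130 mmHg or heart rate below "55 bpm, then cease treatment"; 1C and 1D say the same. Appendix 1H: "Cease treatment then if SBP≥140 mmHg, repeat the Nicardipine IV infusion with a half of the Dose before ceasing treatment".
- **Reduce in steps, then cease.** Appendix 1F: "then HALVE the dose of Clevidipine every 2-10 minutes and then cease treatment". Appendix 1G: "then DECREASE the dose of Nicardipine by 2.5mg/hour every 2-15 minutes and then cease treatment".

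**The concern.** One trigger leads to two different instructions, and the difference does not follow the drug. Appendices 1G and 1H both cover nicardipine with the same 15 mg/h ceiling, yet one tapers and the other ceases. Appendices 1A and 1B also permit a nicardipine infusion, at 5-15 mg/h, under a plain instruction to cease. What happens to a patient on nicardipine who falls below 130 mmHg depends on which table the site uses.

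The protocol itself gives this value its importance. Background section 6 (evidence for early intensive BP lowering) places the risk of BP lowering below 130 mmHg and says that range lies outside what the protocol involves. Under 1F and 1G, however, drug continues by instruction below that level.

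There is also a practical consequence. Section 12 has monitors confirm adherence to the protocol. A site that tapers under 1G follows its appendix but departs from the plain wording of section 6.1.1; a 1G site that ceases at once does the reverse. Neither can be judged against one rule.

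**Working it through.** The plan states no taper duration, so there is no figure of its own to reproduce. The check counts the steps that Appendices 1F and 1G prescribe.

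**Inputs**
- Nicardipine (1G): "Maximum dose = 15 mg/hour"; steps of 2.5 mg/h; interval 2-15 min.
- Clevidipine (1F): maximum 32 mg/h; each step halves the rate; interval 2-10 min.
- Assumption: the last clevidipine step is 2 mg/h, the initiation rate in 1F. The appendix gives no end point, and halving alone never reaches zero.
- Assumption: the first reduction is made at the reading below 130 mmHg, and systolic BP stays below 130 throughout.

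**Duration** = intervals from the first reduction to zero rate × interval length.

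- Nicardipine from 15 mg/h: 12.5, 10, 7.5, 5, 2.5, 0. That is 15 / 2.5 = 6 reductions and 5 intervals. 5 × 2 = 10 min; 5 × 15 = 75 min.
- Clevidipine from 32 mg/h: 16, 8, 4, 2, off. That is 4 halvings, then cessation, and 4 intervals. 4 × 2 = 8 min; 4 × 10 = 40 min.

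**Drug infused during the taper** = sum of the step rates × interval in hours.

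- Nicardipine: 12.5 + 10 + 7.5 + 5 + 2.5 = 37.5 mg/h. 37.5 × 2/60 = 1.25 mg; 37.5 × 15/60 = 9.4 mg.
- Clevidipine: 16 + 8 + 4 + 2 = 30 mg/h. 30 × 2/60 = 1 mg; 30 × 10/60 = 5 mg.

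Under a plain instruction to cease, further infusion is zero.

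**How far the assumptions matter**

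| Variation | Taper duration |
|---|---|
| Nicardipine from 5 mg/h | 2-15 min |
| Nicardipine from 10 mg/h | 6-45 min |
| Nicardipine from 15 mg/h, first step one interval later | 12-90 min |
| Clevidipine from 32 mg/h, last step 16, 8, 4, 2 or 1 mg/h, 10-min interval | 10, 20, 30, 40 or 50 min |
| Clevidipine from 32 mg/h, last step 2 mg/h, first step one interval later | 10-50 min |

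The permitted interval itself spans a factor of 10/2 = 5 in 1F and 15/2 = 7.5 in 1G.

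**Heart rate.** At a rate below 55, 1F and 1G taper while 1B-1D and 1H cease. Section 6.1.1 has no heart-rate rule, so this disagreement is among the appendices only.

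**The case against.** The best defence is that the appendices simply carry out the section's threshold in a way suited to each drug. Section 6.1.1 sets no tempo, sends the reader to the appendices for detail, and both tapers do end in cessation. That reading is possible for clevidipine, which only 1F covers. It does not explain nicardipine, which is tapered in one table and ceased in others over the same rates.

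A second defence is that clinicians are not bound to the slow end of the taper. Appendices 1F and 1G call for readings every 2 minutes during active treatment, sections 6 and 6.1.1 allow changes on clinical judgment, and section 7 calls for allocated management to be stopped or modified where that is in the patient's best interest. This stands as a limit on the minutes. It permits departures from a default rule but does not say what the default is.

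The third defence answers an inference that a reader might draw: that patients at 1F and 1G sites are exposed to more low BP than patients elsewhere. The documents do not support it. The lines in 1A-1D follow bolus instructions, where ceasing largely means giving no further bolus. Table 4 lists durations of action of 3-6 h for labetalol, 3-4 h for urapidil and 1-4 h for hydralazine, against 10 min for clevidipine and 15-30 min for nicardipine. Zero further infusion is therefore not zero further effect. The point is partial, because 1A-1D also allow infusions, but it is enough to bar a claim of greater hazard.

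**Conclusion.** The contradiction is real and stands in current operative text. Of seven appendices with a rule at 130 mmHg, five agree with the plain wording of section 6.1.1 and two do not. Nicardipine has both rules, 1F leaves its halving open-ended, and no text takes precedence.

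The size, taken literally from maximum rate, is 10-75 minutes of further infusion under 1G and about 8-40 minutes under 1F. The 75 and 40 are one worst case per drug. They are not the two ends of a range for a typical patient, and they rest on the longest permitted interval at every step and, for clevidipine, on the assumed last step of 2 mg/h. Lower rates, shorter steps or clinical judgment reduce them; a delayed first step raises them.

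Two further readings go too far. Section 6.1.1 does not say that cessation must be immediate; it gives a threshold and mentions no steps. Nor does any section define a reading below 130 mmHg as a protocol violation, so the difficulty is that adherence has no single standard, not that violations are being missed. The documents do not say how many sites use 1F or 1G, and no endpoint, analysis or power figure depends on the point. It merits correction because two instructions differ at a value the plan itself names as a safety limit.

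**What to change.** The sponsor should reconcile section 6.1.1 with Appendices 1A-1D and 1F-1H in three respects:

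1. Make the action at systolic BP below 130 mmHg consistent, or state any drug-specific exception in section 6.1.1 itself. If a taper is kept for any drug, its end point should be stated.
2. Make the action at heart rate below 55 consistent across the appendices that have one, or give the reason for the difference.
3. State which text governs if the section and an appendix differ.

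Which rule stands is for the investigators to decide; nothing here favours cessation or taper. The cost is a wording change to one sentence of section 6.1.1 and to the affected appendix tables, plus a notice to sites. It needs no new data and no extra staff.

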## Appendix 1H - BP protocol for centres with Nicardipine (Vietnam)

Early intensive BP lowering group	TREATMENT PROTOCOL
INITIAL therapy	
Indication	SBP > 140 mmHg, then at least 2 times, 5 min apart
BP Target	SBP < 140mmHg reached within 60 minutes of Randomisation into the BP arm
Monitoring	
 
• Continuous HR monitoring
 
• Record BP/HR q 5 mins during active treatment, then q 15 min for first hour, q 30 min for next 5 hours , then hourly for next 18h to 24 h (totally for initial 24h), and then every 3h in next 72h
 

Medication	
Nicardipine (Continuous IV Infusion) (requires ICU admission)	
 
• Nicardipine initiation dose: 5 mg/hour continuous IV for the first 15 minutes
 
• If SBP >140 mmHg, increase the dose by 1-2.5 mg/hour every 5 minutes (7.5, 10, 12.5 and then 15 mg/hour)
 
• Maximum dose = 15 mg/hour
 

Nitroglycerin	If SBP > 140 mmHg after treatment maximum dose of Nicardipine Nitroglycerin dose: 1 – 100 µg /min
MAINTENANCE therapy	
BP Target	Maintenance of SBP 130-140 mmHg/72h
Monitoring	Once SBP is under target (confirmed by 4 readings 15 minutes apart): 
 
• Record BP/HR q 30 minutes for 5 hours and then q 1 h for 18 h.
 

Continuous IV treatment prn	IV infusion according to BP level, increasing or decreasing doses depends on BP stability. If SBP exceeds 140mmHg at any point: 
 
• INCREASE the dose of Nicardipine by 2.5 - 5 mg/2 – 5 minutes
 
• If no reaching SBP target, increase IV infusion maintenance doses (amend 1 – 2.5 mg for each dose increase (e.g if maintenance dose of 2.5 mg/h, dose increased will be 3 – 4.5 mg/h)
 
• If SBP is <140mmHg, Keep the dose of Nicardipine
 
• If SBP < 130 mmHg or HR < 55 bpm: Cease treatment then if SBP≥140 mmHg, repeat the Nicardipine IV infusion with a half of the Dose before ceasing treatment. If SBP still >140 mmHg at maximum dose of Nicardipine, Nitroglycerine is able to be amended.
 

*Oral treatment*

When the BP is stable in 4 consecutive recording times (starting at the 20th hour), oral medications are able to be used.

- The patient using BP medication before stroke: previous anti-hypertensives can be used or switch to new suitable anti-hypertensives starting with a half of the dose which was used before stroke
- Patient with no BP medication before stroke: ACEI is prioritized and/or combination therapy of ACEI + diuretics by increasing diuretics prn from low dose.
- Monitoring HR and BP every 3 hrs to 72h

**Note: Monoamine oxidase inhibitors are not recommended with this BP lowering agent and phosphodiesterase inhibitors must not be used with GTN.**

**Key to abbreviations:** ACEI – Angiotensin converting enzyme inhibitor; BP – blood pressure; bpm – beats per minute; HR – heart rate; ICU – intensive care unit; q – every; prn – as required; mg/hour – milligram per hour; µg/Kg/min – micrograms per kilogram per minute; µg/min – micrograms per minute.

